1. OBJECTIVES

1.1 Safety Run In

1.1.1 Primary Objective

To select a safe and tolerated dose schedule (ie: number of consecutive twice daily fractions) of LDFRT + temozolomide based on hematologic toxicity at one month following initiation of therapy.

1.1.2 Secondary Objectives

To estimate the acute and late radiation-associated neurologic toxicity of salvage LDFRT + temozolomide.

1.2 Phase II

1.2.1 Primary Objective

1.2.1.1 To estimate the one year overall survival in patients treated with LDFRT + temozolomide for recurrent HGG.

1.2.2 Phase II Secondary Objectives

1.2.2.1 To estimate the 6 month progression free survival in patients treated with LDFRT plus temozolomide for recurrent HGG.

1.2.2.2 To estimate the rate of pseudoprogression in patients treated with LDFRT plus temozolomide for recurrent HGG

1.2.2.3 To characterize the chronologic sequence of pseudoprogression in patients treated with LDFRT plus temozolomide for recurrent HGG.

1.2.2.4 To estimate the hematologic toxicity of salvage LDFRT + temozolomide.

1.2.2.5 To estimate the radiation-associated acute and long term neurologic toxicity of salvage LDFRT + temozolomide.

2. BACKGROUND

2.1 Study Disease

High grade glioma (HGG) is one of the most lethal forms of human cancer (1). The standard of care at the time of initial diagnosis of HGG consists of surgical resection followed by adjuvant radiation therapy and temozolomide chemotherapy, based on

the results of a randomized controlled trial which demonstrated a significant improvement in overall survival with the addition of temozolomide to adjuvant radiation therapy alone (1). Although this study was performed in patients with GBM, the results are widely applied to patients with anaplastic astrocytoma (AA) who are treated with the same paradigm. Despite recent advances in the treatment of HGG, the diagnosis remains essentially incurable and the tumor will recur in the vast majority of patients.

Management of patients with recurrent HGG remains controversial. Accepted treatment options include temozolomide alone, repeat radiation therapy with concurrent temozolomide, or a clinical trial. The response rate to second line therapies is limited and when effective the durability of response is generally poor. Improvements in salvage therapeutic options for HGG are therefore critical.

2.2 LDFRT Rationale

Numerous studies have shown that the slope of the cell survival curve is greater at very low doses of radiation than at the higher doses of radiation which are conventionally employed in the clinic (2-8). The mechanism behind this phenomenon known as hyper-radiation sensitivity appears to be two-fold. First, low doses of radiation do not induce cellular repair mechanisms such as ATM and mismatch repair that are typically activated with clinically relevant doses of radiation (2,9,10). Second, very small fractions of radiation manage to induce pro-apoptotic pathways without inducing pro-survival cascades that are activated with higher doses (11,12). Studies have shown that hyper-radiation sensitivity persists following multiple fractions of radiation (13) and that the effect is greatest in cells in the G2/M phase. Experiments in glioma cell lines have suggested that the point of maximum radiation hypersensitivity occurs with fractions of approximately 0.4-0.5 Gy.

In spite of these data, low dose fractionated radiation therapy (LDFRT) is not typically employed in the clinic because in order to use it as a primary modality, patients would need to be treated with multiple fractions of radiation per day for many months, and this is not feasible. However, *in vitro* and *in vivo* studies have suggested that LDFRT may be used to potentiate full dose chemotherapy, decreasing the development of resistance found with standard doses of radiation and chemotherapy (11-14). Recent data in U87 glioblastoma cells suggest that LDFRT may be used to sensitize cells to the effects of temozolomide. Specifically, Gupta et al. (15) demonstrated that the slope of the cell survival curve is greater following treatment with temozolomide plus LDFRT (0.5 Gy x 4 fractions, 8 hours apart) compared with temozolomide plus 2 Gy of radiation. The mechanism behind this effect remains to be elucidated.

The concept of low dose fractionated radiation therapy as a chemotherapy-sensitizer has been previously evaluated in humans in the context of early phase clinical trials in other disease sites, and the results have been optimistic. Arnold et al. (16) performed a phase II trial in patients with stage III and IV squamous cell carcinoma of the head and neck in which they used 0.8 Gy fractions of radiation twice daily to sensitize patients to induction chemotherapy with carboplatin and taxol. They enrolled forty

September 29, 2022

patients and report an overall response rate of 82% (13% complete response, 69% partial response), which is better than otherwise expected. In addition, they performed a second phase II trial in the same patient population using 0.5 Gy fractions of radiation twice daily to sensitize cells to carboplatin and taxol, and again report a favorable overall response rate of 88% (38% complete response, 50% partial response) (16). The authors propose further evaluation of the regimen in a randomized controlled trial.

Similarly positive results using LDFRT for chemotherapy sensitization were reported by Regine et al. (17) who performed a phase I/II trial of LDFRT plus gemcitabine in patients with unresectable or metastatic gastrointestinal tumors. The median overall survival time was 10 months, which is better than historical data might predict for these aggressive tumors.

A recent phase 2 trial evaluated ultrafractionated radiation therapy (3 daily doses of 0.75 Gy to a total dose of 67.5 Gy) without temozolomide in patients with newly diagnosed unresectable GBM (Beauchesne 2010). The results of this study were optimistic with no grade III or IV CNS toxicity, and PFS and OS which were superior to conventional RT alone based on historical controls.

Given the promising preclinical and clinical data, the purpose of this trial is to examine the safety and efficacy of LDFRT as a chemo-potentiator of temozolomide in patients with recurrent HGG.

The phase 1 component of the study is completed and all patients are being treated according to cohort 1. In general patients have tolerated treatment well with 5 patients with SAEs attributable to the study treatment (fatigue in 2 patients, and lymphocytopenia, aphasia, cognitive disturbance each in 1 patient). Two of 22 patients had pathologically confirmed radionecrosis.

This unanticipated pseudo-progression type response renders our original primary objective of response rate inappropriate. With this amendment we wish to change the primary objective to one year overall survival and enroll the remaining nine patients. The current one year OS is 45.1% (80% CI: 28.2%, 60.9%), the median OS is 9.5 months (median follow-up of 12.7 months) and the median PFS is 4.0 months. Given that patients on this trial have been treated without any severe toxicities, it would be informative to determine if it is possible that there may be a delayed treatment effect that would indicate further study was warranted. Since overall survival is the most definitive endpoint for a clinical trial, we would like to estimate this outcome with the full sample size of 31 and potentially use this information as a reference in a future

clinical trial.

3. PATIENT SELECTION

3.1 Eligibility Criteria

- 3.1.1 Patients must have recurrent GBM or anaplastic astrocytoma.
- 3.1.2 The diagnosis of GBM or anaplastic astrocytoma must be histologically confirmed.
- 3.1.3 Patients must have been previously treated with surgical resection (any extent okay) and radiation therapy plus temozolomide
- 3.1.4 Patients must be at least 12 months from completion of radiation therapy (to be consistent with the “rechallenge” group from Perry et al. JCO 2010 where the median time from completion of adjuvant radiation therapy to the time of progression was 19.69 months).
- 3.1.5 At least 2 months from completion of temozolomide (to be consistent with the “rechallenge” group from Perry et al. JCO 2010)
- 3.1.6 Because no data regarding the effects of LDRT in patients <18 years of age, children are excluded from this study but will be eligible for future pediatric trials. 18 years.
- 3.1.7 ECOG performance status ≤ 2 (Karnofsky $\geq 60\%$, see appendix A).
- 3.1.8 There must be measurable disease on MRI.
- 3.1.9 Patients must have normal organ and marrow function as defined below:
 - leukocytes $\geq 3,000/\text{mcL}$
 - absolute neutrophil count $\geq 1,500/\text{mcL}$
 - platelets $\geq 100,000/\text{mcL}$
 - total bilirubin within normal institutional limits
 - AST(SGOT)/ALT(SGPT) $\leq 2.5 \times$ institutional upper limit of normal
 - creatinine within normal institutional limits
 OR
 - creatinine clearance $\geq 60 \text{ mL/min}/1.73 \text{ m}^2$ for patients with creatinine levels above institutional normal.
- 3.1.10 If a woman is of child-bearing potential, a negative urine or serum pregnancy test must be demonstrated prior to treatment. Women of childbearing potential and men must agree to use adequate contraception (hormonal or barrier method of birth control; abstinence) for the duration of study participation and

September 29, 2022

for up to 12 weeks following the study. Should a women become pregnant or suspect she is pregnant while participating in this study she should inform her treating physician immediately.

3.1.11 Ability to understand and the willingness to sign a written informed consent document.

3.1.12 Temozolomide re-treatment is planned by the treating neuro-oncologist.

3.1.12 The most recent brain tumor pathology obtained for the patient must be glioblastoma or anaplastic astrocytoma.

3.2 Exclusion Criteria

- 3.2.1 Patients who are unable to receive MRIs will be excluded from the study since MRIs will be critical in monitoring the efficacy of therapy.
- 3.2.2 Patients may not be receiving any other investigational cancer treatment agents at the time of enrollment.
- 3.2.3 Patients may not have previously failed treatment with salvage temozolomide.
- 3.2.4 Patients may not have previously failed treatment with a VEGF inhibitor.
- 3.2.5 Patients may not have previously been treated with >1 course of radiotherapy to the brain.
- 3.2.6 Patients may not have previously been treated with radiosurgery to the brain.
- 3.2.7 Uncontrolled intercurrent illness including, but not limited to ongoing or active infection, symptomatic congestive heart failure, unstable angina pectoris, cardiac arrhythmia, or psychiatric illness/social situations that would limit compliance with study requirements.
- 3.2.8 Pregnant and/or breastfeeding women are excluded. Women of child-bearing potential who are unwilling or unable to use and acceptable method of birth control to avoid pregnancy for the entire study period and up to 12 weeks after the study are excluded. Male subjects must also agree to use effective contraception for the same period as above.

3.3 Inclusion of Women and Minorities

Both men and women and members of all races and ethnic groups are eligible for this trial.

4. REGISTRATION PROCEDURES

Eligible patients will be entered on study centrally at the Johns Hopkins Hospital by the Study Coordinator.

To register a patient, the following documents should be completed by the research nurse or data manager and sent to the Coordinating Center Study Coordinator via fax or email.

- Copy pathology report
- Source documentation verifying eligibility
- Eligibility checklist
- Signed patient consent form
- HIPAA authorization form

If the patient is deemed eligible for the study, the Study Coordinator will register the patient and assign a study number.

5. TREATMENT PLAN

5.1 Temozolomide

All patients will receive temozolomide (150 to 200 mg per square meter for 5 days during each 28 day cycle) for a total of 1 year or until the time of disease progression. After one year of follow-up, further chemotherapy or biologic therapy is permitted at the provider's discretion. Therapy will be recorded, but the patient will not be removed from the study. Risks of temozolomide include nausea, vomiting, infertility, teratogenicity, alopecia, fatigue, headache, constipation, anorexia, convulsions, rash, hemiparesis, diarrhea, asthenias, fever, dizziness, coordination abnormal, viral infection, amnesia, insomnia, lymphopenia, thrombocytopenia, neutropenia, and leucopenia, allergic reactions.

5.1.1 Therapy Modifications

Delay, reduction, or discontinuation of temozolomide administration will be decided according to hematological and non-hematological adverse events (AE), as specified below. If the administration of temozolomide has to be interrupted, radiotherapy will be delayed, as well. Missed doses of temozolomide will not be made up after the end of radiotherapy. Blood work will be checked weekly, based on the discretion of the treating Medical Oncologist.

If radiotherapy has to be temporarily interrupted for technical or medical reasons, unrelated to the temozolomide administration, then treatment with temozolomide may continue.

5.2 Low Dose Fractionated Radiation Therapy (LDFRT)

All patients will receive 0.5 Gy of radiation therapy twice daily (at least 6 hrs. apart). This study will include a safety run-in component. If > 33% of patients in the initial cohort of 6 experience grade 3 or greater hematologic toxicity (attribution of possible or above) according to the NCI Common Toxicity Criteria version 4, then a dose reduction will occur following the schedule listed below. Otherwise, following a 1 month waiting period after the first cycle of adjuvant LDFRT plus temozolomide for the first cohort of patients, the phase 2 study will open for full accrual. Patients will receive radiation with the first six 28-day cycles of temozolomide.

Safety Run-in Dose Reduction Schedule	
Cohorts	Radiation Schedule
Cohort 1	0.5 Gy bid on days 1-5 of temozolomide
Cohort 2	0.5 Gy bid on days 1-4 of temozolomide
Cohort 3	0.5 Gy bid on days 1-3 of temozolomide
Cohort 4	0.5 Gy bid on days 1 & 2 of temozolomide

6 patients will be enrolled in the initial cohort. Dose reduction will occur if >2 patients experience dose limiting toxicity.

5.2.1 Definition of Dose-Limiting Toxicity

Toxicity will be recorded according to the NCI Common Toxicity version 4. Dose limiting toxicity will be considered grade 3 or greater hematologic toxicity (attribution of possible or above) according to this scale. The criteria are available online at the Cancer Therapy Evaluation Program website at:
http://ctep.cancer.gov/protocolDevelopment/electronic_applications/ctc.htm#ctc_40

5.2.2.1.Radiation Treatment Planning

5.2.2.1 Simulation

All patients will undergo CT simulation preferably with intravenous contrast. In addition they will undergo MRI simulation with T1 with gadolinium sequence. They will be treated in a supine position using an aquaplast mask system for immobilization. CT image data will be reconstructed in approximately 3 mm slice thickness and manually co-registered with the T1 post-gadolinium MRI.

5.2.2.2 Target Delineation

The gross tumor volume (GTV) will be contoured using the simulation CT scan and fused T1 with gadolinium sequence MRI. The clinical tumor volume (CTV) will include the GTV plus approximately 0.5-1.5 cm margin. The planning tumor volume (PTV) will include the CTV plus approximately 0.5 cm margin.

5.2.2.3 Normal Tissues

Organs at risk including the eyes, lens, optic nerves, optic chiasm, brainstem, and spinal cord will be contoured on the planning CT scan. Dose to adjacent structures will be limited as much as possible and dose will be recorded. All patients will have been previously irradiated, however the maximum dose delivered in this protocol will be 30 Gy in 0.5 Gy fractions which is below the radiation tolerance typically allowed in patients undergoing repeat irradiation for HGG.

5.2.2.4 Equipment

Patients will be treated using a megavoltage linear accelerator with nominal beam energy of 6 MV.

5.2.2.5 Beam Verification

Either daily on-line cone beam CT guidance or weekly portal imaging will be used for precise patient setup.

5.2.3 Therapy Modifications

For radiation therapy interruptions of up to and including 14 days, irradiation should be completed to the full prescribed dose. On the last day, the total number of fractions and the reasons for interrupting therapy must be documented.

If radiation therapy interruption goes beyond 14 days, the patient will be removed from the protocol treatment. Resumption and completion of additional radiation or chemotherapy treatment will then be at the discretion of the treating medical oncologist and radiation oncologist.

Treatment may be postponed for re-evaluation of disease. Participants may require further biopsies to confirm disease status. If results reveal stable disease, participants will continue protocol intervention.

5.2.4 Risks of Radiation

Short term toxicities of radiation therapy include fatigue, alopecia, erythema or irritation of the skin, dry skin, headaches, worsening of current symptoms, edema of brain requiring steroids, ear pain or discomfort, damage to the baby if patient is or becomes pregnant, seizures, neurologic deficits depending on tumor location, edema of brain requiring surgery, death. Long term toxicities include memory loss, cataracts, edema of the brain requiring steroids, vision loss, hearing loss, necrosis of brain requiring surgery second tumor or cancer caused by radiation.

5.3 Duration of Therapy

In the absence of treatment delays due to adverse events, LDFRT will be administered with the first 6 cycles of temozolomide and temozolomide will continue for a total of 1 year and or until one of the following criteria applies:

- Disease progression,
- Intercurrent illness that prevents further administration of treatment,
- Unacceptable adverse event(s),
- Patient decides to withdraw from the study, or
- General or specific changes in the patient's condition render the patient unacceptable for further treatment in the judgment of the investigator.

5.4 Duration of Follow Up

Patients will be followed until the time of death or until circumstances prevent the patient from presenting for additional follow-up.

5.5 Criteria for Removal from Study

Patients will be removed from study when any of the criteria listed in Section 5.3 applies. The reason for study removal and the date the patient was removed must be documented in the Case Report Form. Patients will continue to be followed for overall survival. Data from medical oncology, including MRI reports and additional chemotherapy, will be collected until time of death.

6. CORRELATIVE/SPECIAL STUDIES

Not applicable.

7. STUDY CALENDAR

See Appendix D. Baseline evaluations and imaging are to be conducted within 4 weeks prior to start of protocol therapy. Every effort should be made to adhere to the protocol timeline as closely as possible, but if studies are delayed or missed as a result of unavoidable conflicts such as hospitalization at an outside facility, deteriorating of patient status, or other adversity precluding presentation for evaluation, it will not be considered a protocol deviation. Toxicity assessments that cannot be done in person will be completed over the phone.

In order to minimize the need for research-only in-person visits, telemedicine visits may be substituted for in person clinical trial visits or portions of clinical trial visits where determined to be appropriate and where determined by the investigator not to increase the participants risks. Prior to initiating telemedicine for study visits the study team will explain to the participant, what a telemedicine visit entails and confirm that the study participant is in agreement and able to proceed with this method. Telemedicine acknowledgement will be obtained in accordance with the Guidance for Use of Telemedicine in Research. In the event telemedicine is not deemed feasible, the study visit will proceed as an in-person visit. Telemedicine visits will be conducted using HIPAA compliant method approved by the Health System and within licensing restrictions.

8. MEASUREMENT OF EFFECT

Patients with measurable disease will be assessed by standard criteria. For the purposes of this study, patients should be re-evaluated approximately every 8 weeks.

8.1 Antitumor Effect

Response and progression will be evaluated in this study using the international criteria proposed by the Response Assessment in Neuro-Oncology Working Group (RANO) (19).

8.1.1 **Definitions**

Evaluable for toxicity. All patients will be evaluable for toxicity from the time of their first treatment with LDFRT.

Evaluable for objective response. Only those patients who have received at least one cycle of therapy, and have had their disease re-evaluated will be considered evaluable for response. These patients will have their response classified according to the definitions stated below. (Note: Patients who exhibit objective disease progression prior to the end of cycle 1 will also be considered evaluable.)

8.1.2

8.1.3 **Methods for Evaluation of Disease**

All baseline evaluations should be performed as closely as possible to the beginning of treatment and never more than 4 weeks before the beginning of the treatment.

The same method of assessment and the same technique should be used to evaluate patients at baseline and during follow-up. Imaging-based evaluation is preferred to evaluation by clinical examination when both methods have been used to assess the antitumor effect of a treatment.

MRI: T1 with gadolinium, T2 and FLAIR sequence MRI techniques should be performed with cuts of 5 mm or less in slice thickness contiguously.

Corticosteroid use: Dosages of corticosteroids will be recorded at baseline as well as follow-up visits and will be incorporated into the response criteria.

Clinical examination: Neurologic deficits and symptoms will be recorded at baseline as well as follow-up visits and will be incorporated into the response criteria.

8.1.4 **Progression-Free Survival**

Progression free survival will be measured from the date of initiation of salvage treatment to the date of documented progressive disease according to the RANO criteria (19).

8.1.5 **Overall Survival (OS)**

OS is defined as the duration of time from start of treatment to time of death from any cause.

8.1.6 **Pseudo-progression**

September 29, 2022

Pseudo-progression will be defined and MRI changes including T1 post-gadolinium, T2 or T2 variants such as FLAIR imaging, with or without clinical deterioration and/or increase in dexamethasone dose which stabilizes or reverses on later evaluations without a change in oncologic intervention.

8.1.7 **Toxicity**

Toxicity will be monitored according to the criteria outlined in section 5.2.1.

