9.1.2.1 Phase II

Amended Primary Objective: Estimate one year OS in patients treated with LDFRT + temozolomide for recurrent GBM.

9.1.2.1.1 Primary Endpoint: OS will be measured from initial salvage starting date to the date of death.

9.1.2.1.2 Secondary Endpoints:

9.1.2.1.1.1 **PFS-6:** The definition of progression will be based on RANO criteria (19). Progression free will be measured from initial salvage starting date to the date of progressive disease is defined (documented).

9.1.2.1.1.1.1 Occurrence of pseudoprogression at any time point will be recorded as a binary variable for each patient (yes/no)

9.1.2.1.1.1.2

Use NCI common toxicity criteria (version 4, see section 5.2.1) to record the toxicity of LDFRT plus temozolomide for each patient associated with the treatment. All patients who receive any amount of LDFRT will be evaluable for toxicity.

1.2.1.1.1.3 Use the RTOG/EORTC acute and late radiation morbidity scoring criteria (see appendix B and C) to record the toxicity of LDFRT plus temozolomide for each patient with recurrent HGG. All patients who receive any amount of LDFRT will be evaluable for toxicity.

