9.3 Statistical Methods of Analysis

9.3.1 **Safety/Toxicity:** NCI CTC version 4.0 will be used for scoring the toxicity and adverse events. The severity and frequency of the toxicity will be tabulated by the tested dose or doses using descriptive statistics. The proportions of patient who experienced grade 3 or above toxicities will be estimated, along with 95%

confidence intervals by each type of toxicity.

9.3.2 Pseudo-progression: The proportion of patients who had pseudo-progression will be reported with 95% confidence intervals.

9.3.2 PFS-6: The definition of progression will be based on RANO criteria (19). Progression free will be measured from initial salvage starting date to the date of progressive disease is defined (documented). The proportion of PFS-6 will be estimated along with 95% confidence intervals using the exact binomial method.

9.3.3 OS: the survival time is defined from the date of treatment start to the date of death. Patients who have not died by the analysis data cut-off date will be censored at their last date known to be alive. The Kaplan-Meier method will be used to estimate one year survival, and median survival along with 80% confidence intervals.

9.3.4 Radiation Toxicity: descriptive statistics will be used to summarize radiation toxicity based on the RTOG/EORTC acute and late radiation morbidity scoring criteria (see appendix B and C) for all patients who had any radiation treatment in this study.

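### PFS is defined three times as time to documented RANO progression, with no mention of death, so a patient who dies before 6 months without documented progression has no PFS event

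*Combined protocol and SAP*

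**What the plan says.** Three places define PFS or PFS-6.

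- Section 8.1.4: "Progression free survival will be measured from the date of initiation of salvage treatment to the date of documented progressive disease", with progression judged by RANO.
- Section 9.1.2.1 (Phase II), secondary endpoints: "Progression free will be measured from initial salvage starting date to the date of progressive disease is defined (documented").
- Section 9.3.2 (the PFS-6 paragraph; the number is used twice) repeats that sentence and adds the estimator: "The proportion of PFS-6 will be estimated along with 95% confidence intervals using the exact binomial method".

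None of them mentions death. No other part of the plan gives a PFS censoring rule or says how to treat death without documented progression.

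OS is handled differently. Section 8.1.5, directly after the PFS definition, reads: "OS is defined as the duration of time from start of treatment to time of death from any cause". Section 9.3.3 adds a censoring rule for patients still alive.

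The corresponding objective, 1.2.2.1, is the first-listed phase II secondary objective: "To estimate the 6 month progression free survival in patients treated with LDFRT plus temozolomide for recurrent HGG".

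**The concern.** An endpoint that ends only at documented progression is time to progression, whatever its label. Under that rule an early death without documented progression is not an event. The analysis is a binomial proportion, so the patient must still be classified. An analyst could score the patient progression-free, drop the patient, or count a failure. The literal text leads towards the first, and nothing in the plan requires the third. The first two make PFS-6 look better than the usual meaning of progression-free survival would.

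Such patients cannot be ruled out. Section 7 excuses evaluations missed because of "deteriorating of patient status, or other adversity precluding presentation for evaluation, it will not be considered a protocol deviation", and the MRI footnotes in Appendix D make a similar allowance for scans. The patients nearest death are therefore the ones most likely to lack a final assessment.

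What is at stake is the meaning and comparability of PFS-6. The primary conclusion is not at stake: the criterion in 9.2.1.2 uses only the lower 80% bound of one-year OS.

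**Working it through.** The plan states no figure that depends on the PFS definition, so there is nothing to reproduce. The check is a reading of the definitions followed by an illustration of size.

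**Definitions side by side**

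| Section | Endpoint | Stated end point | Death named? |
|---|---|---|---|
| 8.1.4 | PFS | documented RANO progression | no |
| 9.1.2.1 (Phase II) | PFS-6 | documented progression | no |
| 9.3.2 (PFS-6) | PFS-6 | documented progression | no |
| 8.1.5 | OS | death from any cause | yes |

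**Inputs.** N = 31 (9.2.1.2). Interim median OS 9.5 months and median PFS 4.0 months (2.3). Interim one-year OS is given as 45.1% in 2.3 and 9.1.1 and as 41.5% in 9.2.1.2; both are used. Let *k* be the number of patients who die before 6 months without documented progression. The documents do not give *k*.

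**Ceiling on *k*.** All deaths before 6 months, assuming exponential survival:

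- From the median: S(6) = 0.5^(6/9.5) = 0.645, so 31 × 0.355 = 11.0 deaths.
- From 45.1% at one year: S(6) = √0.451 = 0.672, so 10.2 deaths.
- From 41.5% at one year: S(6) = √0.415 = 0.644, so 11.0 deaths.

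So about 10 to 11 early deaths are expected, and *k* is only the part of them without documented progression.

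**Base PFS-6 with death as failure (assumed).** 0.5^(6/4.0) = 0.354, and 31 × 0.354 = 11.0, so take 11/31 = 35.5%. The 4.0-month median may itself use the progression-only definition, so other bases are tried below.

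**Shift for each handling.** If scored progression-free, PFS-6 = (11 + *k*)/31, a shift of *k*/31. If excluded, PFS-6 = 11/(31 − *k*).

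| *k* | Failure | Scored progression-free | Excluded |
|---|---|---|---|
| 1 | 11/31 = 35.5% | 12/31 = 38.7% (+3.2) | 11/30 = 36.7% (+1.2) |
| 2 | 11/31 = 35.5% | 13/31 = 41.9% (+6.5) | 11/29 = 37.9% (+2.4) |
| 3 | 11/31 = 35.5% | 14/31 = 45.2% (+9.7) | 11/28 = 39.3% (+3.8) |

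**Other bases.** The progression-free shift, *k*/31, does not depend on the base. For exclusion:

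- Base 6/31 = 19.4%: 6/30 = 20.0% (+0.6) at *k* = 1; 6/28 = 21.4% (+2.1) at *k* = 3.
- Base 14/31 = 45.2%: 14/30 = 46.7% (+1.5) at *k* = 1; 14/28 = 50.0% (+4.8) at *k* = 3.

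**Sampling error.** Exact (Clopper-Pearson) 95% intervals: 11/31, 19.2% to 54.6%; 12/31, 21.8% to 57.8%; 14/31, 27.3% to 64.0%.

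**The case against.** The strongest reply is that this is an omission and not an instruction. The endpoint is called progression-free survival, and few analysts would call a patient who is dead at 6 months progression-free. Nothing in the plan tells anyone to do so. RANO is cited but not reproduced, so the documents cannot show how much decline before death it would capture.

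The affected group may also be empty. Re-evaluation is about every 8 weeks. Clinical decline can count towards progression: "Neurologic deficits and symptoms will be recorded at baseline as well as follow-up visits and will be incorporated into the response criteria", and steroid dose is treated the same way. After removal from study, "Data from medical oncology, including MRI reports and additional chemotherapy, will be collected until time of death". A median PFS of 4.0 months against a median OS of 9.5 suggests that progression is usually documented well before death. For *k* to reach 3, 3/11 = 27% of the expected early deaths would have to lack documented progression, and nothing in the plan supports that share. Finally, PFS-6 is secondary and has no decision rule.

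Most of this stands, and it limits the size and weight of the point. It does not remove it. Three operative definitions agree with each other, and a label does not override them, least of all when the adjacent OS definition names death explicitly. Close follow-up makes *k* small but does not guarantee zero, given the tolerance for missed evaluations. The choice of denominator is not in dispute: objective 1.2.2.1 points to all treated patients, which makes exclusion hard to defend.

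**Conclusion.** The point holds. As written, PFS is time to documented progression, and the stated rule gives no event to a patient who dies before 6 months without it. Relative to counting the death as a failure, PFS-6 is biased upward, or unchanged if there are no such patients. Each affected patient adds 3.2 points if scored progression-free. Exclusion adds about 0.6 to 1.5 points for one patient over bases of 6/31 to 14/31, and 2.1 to 4.8 for three.

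The omission is certain from the text. Its effect is not: *k* is unknown, the base and the ceiling rest on exponential curves fitted to interim figures, and every illustrated shift is smaller than the sampling error with 31 patients. The confidence interval does not reflect this bias. It should be corrected, but the sample size, the one-year OS analysis and the go-forward criterion do not depend on it.

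**What to change.** In 8.1.4, 9.1.2.1 (Phase II) and 9.3.2 (PFS-6), use one definition: time from the start of protocol treatment to RANO progression or death from any cause, whichever comes first. In 9.3.2 add that a death before 6 months counts as not progression-free and that the denominator is all treated patients, in line with objective 1.2.2.1.

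It would also help to report how many patients are alive with unknown progression status at 6 months. Counting them as failures is one conservative option, and a Kaplan-Meier estimate could be added as a supplement. Neither is essential to the correction.

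The cost is wording in three places. No new data are needed, because survival and MRI reports are already collected until death (5.5). The reported PFS-6 may be slightly lower.
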